Short version of the final protocol

(Ver 6, Aug 31, 2018)

Introduction

Every year more than 250,000 patients are admitted in the Capital Region of Denmark. During admissions, the clinical track and trigger system "Early Warning Score (EWS)" is used to systematically observe and detect acutely deteriorating patients. The system is designed to prevent serious adverse events like unanticipated transfer to the intensive care unit, cardiac arrest and unexpected death. EWS consists of standardized measurements of the patient's vital signs and an escalation protocol that determines further actions based on the aggregated EWS score. At admission, and as a minimum twice a day, nurses measure vital signs on all hospitalized patients. Depending on the predetermined cut-off values (i.e. heart rate above 150 bpm = 3 points) an aggregated score is calculated. Based on the total score, the escalation protocol determines the time interval for the next measurement as well as a clinical action (i.e. call for attending doctor). EWS is developed to detect and to treat potentially deterioration of disease that might lead to critical illness and death. In its current form, there is only limited room for individual clinical assessment. A standardized track and trigger system like EWS does not differentiate between different types of disease or the patient's individual physiological response. Therefore, there is a potential risk that the system fails to detect a patient with an abnormal stress response. Additionally; patients suffering from chronic illness might have different normal values than healthy patients, leading to unnecessarily excess observation, measurement, and suboptimal usage of limited staff resources.

Further improvement and optimizing of the EWS track and trigger system is necessary, as there is potential to improve patient care and use staff resources more appropriate. The current study will examine the effect of a new Individual EWS (I-EWS) with incorporated clinical assessment using the staff's professional experience and providing even more personalized observation and treatment.

Aim of the study

The aim of the study is to investigate the impact of the I-EWS that has a systematic involvement of clinical assessment and the possibility to adjust the score, whilst keeping the same escalation protocol. I-EWS will be compared to the existing EWS with a focus on mortality, critical illness, and the use of staff resources.

Hypothesis

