The main hypothesis is that I-EWS will be non-inferior to the existing NEWS algorithm regarding 30-day mortality, but the introduction of clinical assessment results in fewer I-EWS scores per patient per day than with NEWS.

Method

The study is a prospective, cluster randomized, cross-over, non-inferiority study. The participating eight hospitals are randomly assigned to six and a half months with either I-EWS or the existing EWS track and trigger system. Computer generated numbers are used to randomize the hospitals to either the intervention or control arm of the study. A single cross-over will take place resulting in a total study period of 13 months. I-EWS is only available at hospitals assigned to I-EWS (Grey areas in the figure below). All EWS scores and subsequent actions are documented in real time. Each period will start with 14 days of implementation, and before cross-over patients will be followed by an observation period of 30 days (indicated by shaded areas below).

Hospital	1 period: 6 ½ months	2. period: 6 ½ months
Herlev & Gentofte Hospital (2 units)	Cluster 1	Cluster 1
Amager og Hvidovre Hospital (2 unit)	Cluster 2	Cluster 2
Nordsjællands Hospital (2 units)	Cluster 3	Cluster 3
Bispebjerg Hospital (1 unit)	Cluster 4	Cluster 4
Glostrup Hospital (1 unit)	Cluster 5	Cluster 5
Sjællands Universitetshospital (2 units)	Cluster 6	Cluster 6
Slagelse Hospital (1 unit)	Cluster 7	Cluster 7
Holbæk Hospital (1 unit)	Cluster 8	Cluster 8

Intervention: Prior to project start ambassadors from all the participating wards will receive 2 hours of education depending on which EWS their hospital is randomized to use. Hospitals randomized to use I-EWS will receive an introduction course and hospitals using EWS will receive a brush-up course. Subsequently, they will be responsible for teaching at their respective wards. I-EWS, like the current EWS, will apply systematic observation, where patients continue to be evaluated according to vital signs and assigned a score of 0-20. The innovation in I-EWS is that SP systematically calls for staff to reassess the assigned score after they have entered the patient's vital signs. Afterwards it is possible to adjust the score by a maximum of +6 or -4. Nursing staff reevaluate when vital signs and clinical assessment are compared, whether the patient is in the correct observation range, and if the clinical actions defined for this range is relevant.

Ethics

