- 1. ≥18 years at admittance at participating hospital
- 2. Admittance in a department/Ward using systematised EWS
- 3. Admittance for more than 24 hours

Patients will be included at the first admission in the study period (index admission) and will remain in this group (intervention/control) for a follow-up period of 30 days. All subsequent admissions (readmissions) will be ignored.

Exclusion

- 1. Patients arriving at the gynaecological-, obstetric-, and paediatric department
- 2. If a "do not resuscitate"-order or "no NEWS/I-EWS registration" are identified, patients will be excluded for further analysis at the time of registration.

Definition of clusters

Eligible hospitals can consist of one or two units. A hospital is defined based on its administrative organisation and catchment area. Each hospital will generate one cluster and two (time) periods (control and intervention). See schematic figure 1 below

Randomisation

Prior to the study start participating clusters will be randomised to start as either intervention or control. Eight cluster will be available, and we will be using stratified randomisation based on size of hospitals (number of unique admissions, more than 25,000 admissions is defined as large hospitals, less than 25,000 is small hospitals), to balance a potential size difference between the intervention and control group. The randomization will be performed using computer-generated numbers. The randomisation will allocate participating hospitals to periods of intervention or control in a 1:1 ration. A cross-over will occur after 6.5 months and is expected to be at April 15, 2019.

Ethics

The study was presented to the Regional Ethics Committee, who decided that no formal approval was needed in accordance with Danish law (J.nr. 1701733). Data management has been approved by the Danish Data Protection Agency (ID: HGH-2017-116, I-suite:06030).

Study variables:

The following data are collected as a minimum for the included patients:

- Age and gender
- Personal Identification number (Danish Civil Registration number (CPR)

- Presence of Do Not Resuscitate (DNR) order
- Presence of "No EWS registration"
- EWS/I-EWS Scores
- Registered actions to the EWS/I-EWS escalation protocol
 - Responsible nurse contacted
 - Treatment plan already made
 - Doctor contacted
 - MET contacted
 - Other
 - Charlson Comorbidity Index

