Table of summary statistics for patients and at hospital or cluster level for each group (intervention or control) will be presented with baseline variables (Number of patients, number of admissions, age, sex, Charlson Comorbidity index, hospital characteristics) Continuous variables will be summarized with: n (based on non-missing sample size), mean, standard deviation, median, interquartile range, number of missing values. Categorical variables will be reported as frequency and percentages (based on non-missing sample size) and number of missing values. Continuous and ordinal variables will be tested by Wilcoxon analysis or t-tests as appropriate for differences between groups. Categorical variables will be tested with chi-square.

Primary outcome analysis

The primary outcomes will be an **analysis of all-cause mortality and NEWS/I-EWS scores per patient per day between the intervention and control group**. Patients will be followed as one cohort and data will be analysed as randomized and in accordance with the intention-to-treat principle.

Inclusion: Patients will be included at the first admission at the participating hospitals in the study period (index admission) and will remain in this group (intervention/control) for follow-up of 30 days. Admission is defined as a contact to a hospital with a duration of more than 24 hours. All subsequent admissions (readmission) will be ignored. Any patient lost to follow-up will be censored at the last time known to be alive.

The main analysis of the primary outcome for motality will be done using logistic regression that accounts for clustering with adjustment for hospital ID, age, and sex. Intraclass correlation

coefficient with 95% confidence intervals will be reported. Results will be presented at the individual patient level. Assessment of cluster-level differences will be performed. NEWS/I-EWS scores per patient per day will be compared using linear regressions.

Each period will start with 14 days of implementation, and before cross-over patients will be followed by an observation period of 30 days Periods of implementation and observation will be censored in the analyses (patients admitted in these periods will not be included in the analyses). Cumulative incidence plots (1-survival) will be calculated using the Kaplan-Meier method and presented.

Sensitivity analyses of the primary endpoint

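### The mortality model leaves out the Charlson index, which is already collected; this costs precision and leaves chance case-mix imbalance, but does not cause systematic bias

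*SAP*

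**What the plan says.** SAP, Primary outcome analysis: the main mortality model is a "logistic regression that accounts for clustering with adjustment for hospital ID, age, and sex". No other covariate is named, and no period term.

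SAP, Study variables: under "The following data are collected as a minimum for the included patients", the list includes the "Charlson Comorbidity Index" and, for scores, only "EWS/I-EWS Scores". Historical contacts and diagnoses are also drawn from the national patient register, so comorbidity before the index admission can be constructed.

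SAP, Baseline description of groups: Charlson is one of the "baseline variables (Number of patients, number of admissions, age, sex, Charlson Comorbidity index, hospital characteristics") to be tabulated and tested between groups. It is used nowhere else.

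SAP, Sensitivity analyses of the primary endpoint: the listed analyses are per-protocol, without transferred patients, last three months of each intervention period, and without non-adherent departments. None adds a case-mix covariate. Under Secondary endpoints, 2-day and 7-day mortality inherit the primary model.

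On the score itself, the Introduction to the short protocol says: "At admission, and as a minimum twice a day, nurses measure vital signs on all hospitalized patients". Its Method section says the I-EWS system "systematically calls for staff to reassess the assigned score after they have entered the patient's vital signs".

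**The concern.** Treatment is allocated to hospital-periods, so the patients of one hospital in its two arms are admitted at different times of year. Hospital ID removes stable differences between hospitals. It cannot remove a change in patient mix within a hospital from one period to the next, and age and sex capture only part of such a change. With eight hospitals of very unequal size, hospital-specific changes average out poorly.

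What is at stake is the precision of a non-inferiority comparison with a 0.5-point margin on a 2.9% event rate, and how the result is read if the baseline table shows a Charlson difference. With about 75,000 patients per arm, small differences will reach significance in the planned baseline tests. Without a prespecified adjusted model, any response to such a difference would be chosen after the data are seen.

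**Working it through.** **Inputs.** From the SAP, Sample size calculation: mortality 2.9%, margin 0.5 percentage points (taken as absolute), 150,000 patients, true effect 0, power above 90%, 25% variation in mortality over the year. From Randomisation: eight clusters, 1:1, stratified at 25,000 admissions. From the hospital table at the end: 2016 volumes, whose eight rows sum to 189,905. Assumed: 75,000 per arm and one-sided 0.025, since the SAP gives P < 0.05 without sidedness.

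**1. The plan's own figure.** Without clustering, SE = √(2 × 0.029 × 0.971 / 75,000) = 0.00087, or 0.087 points. Power = Φ(0.005/0.00087 − 1.96) = 99.99%. The stated power above 90% is met. It would stay so up to a design effect of 75,000/23,671 = 3.2, where 23,671 is the number per arm for 90% power.

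**2. A change shared by all hospitals.** Four hospitals exceed 25,000 admissions and four do not. Two from each stratum start with I-EWS, giving 6 × 6 = 36 allocations. If share s of the volume starts with I-EWS and mortality differs by a relative amount r between periods, the arm difference is 2.9 × r × (2s − 1) points. Over the 36 allocations s runs from 0.422 to 0.578.
- r = 25% (the whole annual variation placed between the periods): mean 0, median absolute value 0.04, maximum 2.9 × 0.25 × 0.155 = 0.11 points.
- r = 10%: maximum 0.05 points.

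Shared changes therefore largely cancel; unequal hospital sizes leave the remainder.

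**3. Changes specific to a hospital.** Let residual mortality vary between hospital-periods with coefficient of variation CV (assumed). With volume shares w, Σw² = 0.154, and SE = √(0.00087² + 2 × (0.029 × CV)² × 0.154).

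| CV | SE (points) | Power |
|---|---|---|
| 0 | 0.087 | 99.99% |
| 5% | 0.118 | 98.8% |
| 7.5% | 0.149 | 92.0% |
| 10% | 0.183 | 78.2% |

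This is the component that case-mix covariates can reduce. Charlson removes only its comorbidity part, and the documents do not say how large that part is.

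**4. Size of a comorbidity imbalance.** If each Charlson point multiplies the odds of death by k, and death is rare enough to read odds as risk, a residual arm difference of 0.1 point shifts mortality by 2.9 × (k^0.1 − 1):
- k = 1.2: 0.053 points
- k = 1.3: 0.077 points
- k = 1.4: 0.099 points

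That is about 11% to 20% of the margin. Both k and the 0.1 point are assumptions.

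A second illustration assumes 30% of patients have high comorbidity with mortality ratio R of 2 to 4. A prevalence difference d between arms shifts mortality by 2.9 × d(R − 1)/(1 + 0.3(R − 1)): 0.02 to 0.05 points for d = 1 percentage point, 0.04 to 0.09 for d = 2, and 0.11 to 0.23 for d = 5.

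**5. How plausible is 0.1 point?** With independent hospital-specific changes, the arm difference has an SD of √0.154 = 0.39 times the typical change within a hospital. A difference of 0.1 at one SD needs typical changes of 0.1/0.39 = 0.26 Charlson points between periods, beyond age and sex. The documents give no Charlson distribution against which to judge this.

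**The case against.** Hospital, age and sex form a clear prespecified covariate set, and no figure in the SAP is shown to be wrong. The order is randomised, each hospital is its own control, and age and sex already absorb some of the comorbidity difference. Power stays above 90% at a residual CV of 7.5%. All of this stands, and it limits the point to efficiency and protection against chance. It does not explain why a prognostic variable already held for included patients should stay out of every model.

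Two stronger readings are tempting, and the documents support neither.

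- **Seasonal case mix biases the contrast.** A reader might infer this from the 25% annual variation, or from the rule that each patient enters once at the first admission, which could place frequently admitted patients in the first period. Both would act mainly as changes shared by all hospitals. Under the randomised cross-over such changes have mean zero over allocations and largely cancel (step 2). For a shared change the direct remedy is a period term, which the SAP does not name. Charlson is no substitute for it, and a common period term does not remove hospital-specific changes in comorbidity.
- **An unmodified admission score is available in both arms.** A reader might infer this because vital signs are measured at admission and I-EWS staff "reassess the assigned score after they have entered the patient's vital signs". The data list names only "EWS/I-EWS Scores". The Endpoints section shows that control-arm scores can also be changed, through temporary or chronic acceptable values. That a comparable raw score is stored in both arms is an inference.

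Two practical objections also stand. Scores can be missing, as the per-protocol definition anticipates, so a score covariate would lose patients or need imputation. And adding covariates to a logistic model changes the conditional odds ratio, whereas the margin is an absolute risk difference. The fix has to deal with both.

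**Conclusion.** The point holds as an inexpensive improvement to the analysis, not as a threat to validity. Charlson is collected, can be built from diagnoses before the index admission, and enters no model. Chance hospital-specific differences in comorbidity beyond age and sex therefore stay in the mortality contrast and reduce its precision.

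The gain cannot be computed, because the documents give neither the distribution of Charlson nor its prognostic strength here. The only sizes available rest on assumptions: a shift of about 0.05 to 0.10 points for a residual imbalance of 0.1 Charlson point at odds ratios of 1.2 to 1.4, and the power table for assumed residual CVs. The SAP's stated power is not contradicted.

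**What to change.** - In Primary outcome analysis, add the Charlson index to the mortality model alongside hospital, age and sex. State that it is computed from diagnoses recorded before the index admission, how it is coded, and how patients without register history are handled.
- Report the adjusted result as a standardised risk difference with its confidence interval, so that it can be read against the 0.5-point margin.
- Two-day and 7-day mortality need no separate wording, since Secondary endpoints already applies the primary model to them.
- Use a first vital-signs-only score in a supporting model only, and only if data management confirms that it is stored before any modification in both arms (I-EWS adjustment or acceptable values). State how missing scores are handled.
- Consider a period term separately; Charlson does not do its work.

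The cost is a few lines of SAP text and some programming. Charlson needs no new data collection. The score model needs one check of what the record system stores.

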The study is designed as a non-inferiority study to show that I-EWS is not inferior to the existing EWS algorithm with a non-inferiority margin (Δ) of 0.5% regarding 30-day all-cause mortality. The participating hospitals will admit 189,000 individual patients within one-year, individual sizes (admissions) are described on p.12. The sample size is based on the following assumptions: I) within a the inclusion period of ten months, the participating hospitals are expected to admit 150,000 individual patients II) mean all-cause mortality is 2.9% with variations as described on p. 11, III) a variation in mortality of 25% over the course of the year. The non-inferiority margin is set at 0.5%, and if the intervention has an effect of 0, the study has above 90% power to confirm noninferiority. In a previous cohort of 103,733 patients the mean (SD) number of scores per patient per day was 2.3 (2.0) and 15.4% of patients had one NEWS score of ≥ 6 . With the expected

inclusion, we will be able to detect a difference of 0.04 in mean number of scores and a difference of 0.6% in the number of patients with one NEWS \geq 6 with a power > 90%.

Study end

The follow-up for all patients ends after at total study period of 13 Months and is expected to end at the October 31, 2019.

Statistical plan for main outcome paper

Statistical analyses will be performed using SAS and R. Reporting of results will be in accordance with the CONSORT criteria with extension to cluster randomised trials. Analyses will be done using R. P < 0.05 will be considered statistically significant.

Consort diagram

A modified CONSORT trial profile will be used to describe patient flow and total number patients in each group and at each cluster. All patients not included in analysis will be explained.

Baseline description of groups:

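### With eight hospitals, the planned clustered logistic model gives no reliable confidence interval for the 0.5-point mortality comparison if run with routine large-sample errors

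*SAP*

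**What the plan says.** Under Randomisation: "Eight cluster will be available, and we will be using stratified randomisation based on size of hospitals". Each hospital crosses over once, so there are 16 hospital-periods.

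Under Primary outcome analysis, mortality is to be analysed by "logistic regression that accounts for clustering with adjustment for hospital ID, age, and sex". An intraclass correlation is to be reported with its interval. The Secondary endpoints section applies the same analysis to 2-day and 7-day mortality.

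Under Statistical plan for main outcome paper: "P < 0.05 will be considered statistically significant". No sidedness or confidence level is given for the non-inferiority test.

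Under Sample size calculation, the target is a "non-inferiority margin (Δ) of 0.5% regarding 30-day all-cause mortality", with the claim that "if the intervention has an effect of 0, the study has above 90% power to confirm noninferiority". That section also assumes that mortality varies by 25% over the year.

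Nowhere does the SAP name a variance estimator, degrees of freedom, a small-sample correction, a period term or a hospital-by-period effect for this model.

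**The concern.** The sentence has two routine readings, each with normal critical values. One uses hospital fixed or random intercepts with model-based errors. It assumes that hospital mortality rates move in parallel between the two periods. The other uses robust errors clustered on hospital. It needs many clusters, and there are eight of very unequal size (6,598 to 41,420 admissions in the table at the end of the SAP).

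The main safety claim is that I-EWS does not raise mortality by more than 0.5 points. An interval that is too narrow makes that claim too easy to reach when it is false. An interval that is too wide can make a true claim unreachable. The SAP's stated purpose is to clarify the analyses, so this is the place to settle the matter.

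**Working it through.** **Inputs from the SAP.** Margin 0.5 points; "mean all-cause mortality is 2.9% with variations as described on p. 11"; "the participating hospitals are expected to admit 150,000 individual patients", taken as 75,000 per arm; hospital sizes and deaths from the final table. Rates are recomputed as deaths over admissions (2.48% to 3.92%, overall 5,569/189,905 = 2.93%).

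**Inputs assumed.** Non-inferiority is judged by the upper limit of a two-sided 95% CI (one-sided 2.5%). ρ is the correlation of a hospital's rate between periods. Age and sex are not simulated.

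**1. The plan's power figure.** With patients treated as independent, SE = √(2 × 0.029 × 0.971 / 75,000) = 0.000867. Then 0.005/0.000867 − 1.96 = 3.81, so power is 99.99%. This agrees with a figure above 90%.

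**2. Between-hospital variation.** The variance of the eight rates is 2.88 × 10⁻⁵. Mean sampling variance is 0.17 × 10⁻⁵, leaving σ² = 2.71 × 10⁻⁵. The ICC is 2.71 × 10⁻⁵ / (0.0293 × 0.9707) ≈ 0.00095. A second estimate from the same table gave 0.00089. With w as each hospital's share of patients, Σw² = 0.154, equivalent to 1/0.154 ≈ 6.5 equal hospitals.

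**3. Model-based errors, closed form.** At the margin the model counts V = (0.029 × 0.971 + 0.034 × 0.966)/75,000 = 8.13 × 10⁻⁷. It leaves out E = 2σ²(1 − ρ)Σw². False non-inferiority is Φ(−1.96/√((V+E)/V)), ignoring any seasonal shift.
- ρ = 1.0: E = 0, giving 2.5%.
- ρ = 0.9: E = 8.33 × 10⁻⁷, ratio 2.02, Φ(−1.38) = 8.4%.
- ρ = 0.8: E = 16.7 × 10⁻⁷, ratio 3.05, Φ(−1.12) = 13.1%.

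**4. Clustered errors with z.** Using 1.96 where t is needed already gives P(T > 1.96) = 4.5% on 7 df and 4.9% on 6 df. Downward bias of the robust variance with few unequal clusters adds to this.

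If period is left out, the effect reverses. A 25% difference is about 0.25 × 2.93 = 0.73 points within each hospital, with sign set by sequence. The robust error reads this as noise of about √0.154 × 0.73 = 0.29 points. The half-width from this source alone is 1.96 × 0.29 ≈ 0.56 points, more than the margin.

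**5. Simulation at a true +0.5 points.** This uses 36 stratified allocations, the table's sizes scaled to 150,000, and 20,000 trials per scenario on hospital-period risks. Separate logistic fits (3,000 to 10,000 trials per scenario) served as a cross-check.

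| Analysis | Setting | False non-inferiority |
|---|---|---|
| Clustered, z, no period term | no period shift | about 5-7% |
| Clustered, z, no period term | 10% period difference | 0.6-4.4% |
| Clustered, z, no period term | 25% period difference | near 0% (power about 22-34%) |
| Clustered, z, period modelled | any | about 6-9% |
| Model-based, hospital effects | ρ = 1, little seasonal shift | about 3% |
| Model-based, hospital effects | ρ = 0.9 | about 9-10% |
| Model-based, hospital effects | ρ = 0.8 | about 13-16% |
| Hospital-level t, 6 df | all | about 2-3% |

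The logistic fits agree. Model-based errors gave 2.8%, 7.3% and 16.9% at hospital-by-period SDs of 0, 0.05 and 0.10 on the log-odds scale. ρ = 0.9 corresponds to about √(0.1 × 2.71 × 10⁻⁵)/0.0285 ≈ 0.06. Putting t on 6 df onto a clustered error with period modelled still left 3.5-4.2%.

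**6. Power of the 6-df analysis at zero effect.** About 94-96% with parallel rates, 84-88% at ρ = 0.9 and 73-77% at ρ = 0.8.

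**The case against.** A reader might infer that the planned interval is always too narrow, with false non-inferiority about three times nominal. The SAP does not support this. The threefold figure for clustered errors needs a period term that the SAP does not list. As written and with no period shift, the excess is about twofold. With a large period shift, the clustered interval is too wide. The SAP's 25% is variation over the year, so using all of it as a difference between periods is an upper case. At 10% the rate lies on either side of nominal.

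It is also fair that nothing shows hospital rates failing to move in parallel. The table covers one year, and ρ of 0.9 or 0.8 is assumed. The ICC comes from crude rates, and adjustment for age and sex may shrink it. The 2.5% level is a reading of P < 0.05; a one-sided 5% reading would be more lenient still. The sentence does not exclude small-sample inference.

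All of this limits the size of the claim. It does not make the sentence adequate. Parallel rates are not shown either, and the choices left open have false-positive rates from near 0% to about 16%. The conservatism under an omitted period term is an accidental offset that disappears once period is modelled.

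**Conclusion.** The point holds in conditional form. With eight hospitals, neither routine large-sample reading of the mortality model reliably holds a one-sided 2.5% level at the 0.5-point margin. Clustered errors with z err towards false non-inferiority or towards excessive width, depending on the period shift and on whether period is modelled. Model-based errors are near nominal only if hospital rates move in parallel and the seasonal shift is small. A 6-df hospital-level analysis stayed at about 2-3% throughout.

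The sizes rest on the 95% CI reading, the table's sizes and crude rates, 150,000 patients, an ICC of about 0.0009 and the assumed ρ. This is more than an omitted detail, because following the sentence with standard software gives error bars that can be wrong in either direction.

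**What to change.** In Primary outcome analysis, state that the mortality interval comes from a model with arm, period, hospital and a hospital-by-period random effect, adjusted for age and sex, with a named small-sample degrees-of-freedom method. An alternative, though not an identical analysis, is to regress the eight within-hospital period differences in age- and sex-adjusted risk on sequence, with t on 6 df. State the confidence level and sidedness. Use the same inference for 2-day and 7-day mortality.

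A permutation test is not a substitute at one-sided 2.5%. Four large and four small hospitals give 6 × 6 = 36 allocations, so the smallest one-sided p is 1/36 = 0.028.

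The cost is SAP wording, modest code and a wider interval: the critical value alone adds 2.447/1.96 − 1 = 25%. Power falls as shown in step 6. Weighting hospitals by size recovers part of it, up to about 92% at ρ = 0.9. The power statement in Sample size calculation should therefore be qualified, with the assumed ICC and between-period correlation given. The choice should be fixed before outcome data are available.
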